| PDI | Planned dose intensity |
| PK | Pharmacokinetics |
| PLT | Platelet |
| PPS | Per - protocol set |
| PR | Partial response |
| PROMIS | Patient reported outcomes measurement information |

| | |
|------|----------------------------------|
| | system |
| PS | Performance status |
| PT | Preferred term |
| PTE | Pre-treatment event |
| QD | Once daily |
| QOD | Once every other day |
| RBC | Red blood cell |
| RDI | Relative dose intensity |
| SAE | Serious adverse event |
| SMQ | Standard MedDRA query |
| Cr | Creatinine |
| SOC | System organ class |
| SS | Safety analysis set |
| TBIL | Total bilirubin |
| TEAE | Treatment emergent adverse event |
| TP | Total protein |
| TTNT | Time to new treatment |
| TTR | Time to response |
| UA | Uric acid |
| WBC | White blood cell |

2. Introduction

The objective of the BN101-201 study is to evaluate the efficacy and safety of BN101 in the patients with cGVHD who have previously been treated with one to five prior lines of systemic therapy.

This Statistical Analysis Plan (SAP) describes data-handling and statistical procedures to be used for the analysis and reporting of efficacy and safety data collected under Study BN101-201 and presented in the clinical study report (CSR). This SAP has been developed and finalized prior to locking the clinical database. Pharmacokinetic (PK) analyses will be described in separate documents.

3. Study Objective

Primary objective:

- To evaluate the efficacy and safety of BN101/belumosudil in subjects with cGVHD who had previously been treated with at least 1 prior line of systemic therapy.

Secondary objective:

- To evaluate the PK profile of BN101/belumosudil in subjects with cGVHD who had previously been treated with at least 1 prior line of systemic therapy;
- To evaluate other efficacy endpoints of BN101/belumosudil in subjects with cGVHD who had previously been treated with at least 1 prior line of systemic therapy.

Exploratory objective:

- To evaluate changes in the Patient-Reported Outcomes Measurement Information System (PROMIS) Global Health sub-scores of physical and mental functioning

4. Study Design

BN101-201 is a phase 2, multicenter, open label, single-arm study in patients with cGVHD who have previously been treated with one to five prior lines of systemic therapy. It intends to enroll 30 Chinese cGVHD patients and to evaluate the efficacy, safety, and PK profile of BN101/belumosudil in Chinese cGVHD patients.

The study enrollment period is estimated to be 6 months. 6 months after the last patient enrollment, the database will be locked and the primary analysis will be conducted. After primary analysis, all patients will be followed up for additional 6 months and a follow up analysis will be conducted 12 months after the last patient enrollment.

Eligible patients who have signed informed consent will be enrolled to receive BN101/belumosudil (every 28-day cycle) until cGVHD progression, intolerable toxicity, initiation of a new cGVHD therapy, recurrence of hematological neoplasm, loss to follow-up,

withdrawal of consent, or death, whichever occurs first. During study, concomitant treatment with standard of care systemic cGVHD therapies such as corticosteroids, calcineurin inhibitors (tacrolimus, cyclosporine), sirolimus, MMF, or extracorporeal photopheresis (ECP), are permitted as long as the patient has been on a stable dose / regimen of these per the eligibility criteria. Initiation of new systemic cGVHD therapy while on study is not permitted. Response criteria will be assessed after cycles 1, 2, 3 and 4 and then after every other cycle thereafter (i.e. on Day 1 of Cycle 2, 3, 4, 5, 7, 9, 11 etc). For patients assessed as "Lack of Response - Mixed" and "Lack of Response - Progression" [Evaluated by the investigator based on the National Institutes of Health (NIH) Consensus Development Project on Criteria for Clinical Trials in cGVHD(2014), hereinafter referred to as the NIH Consensus Criteria (2014)], if the investigator believed that these patients could continue to benefit from treatment with BN101/belumosudil, the treatment may be continued after a written application was submitted, and approval from the Sponsor's Medical Monitor as well as documentation of the patient's willingness to continue treatment was obtained. For patients who did not achieve any response after 12 cycles of BN101/belumosudil treatment, they should discontinue the study medication and withdraw from the study if in the investigator's judgment there is no evidence of clinical benefit (e.g., improvements in organ score, improvements in Lee symptom scores, reductions of corticosteroid/tacrolimus doses). For patients whose cGVHD has not progressed at the time of discontinuation of the study treatment and who come off study for reasons other than AEs should be tapered off BN101/belumosudil by reducing the dose every other week (200mg QD → 200mg QOD → discontinue).

5. Study Endpoints

5.1. Efficacy Endpoints

5.1.1. Primary Efficacy Endpoints

The primary efficacy endpoint is the overall response rate (ORR) as assessed by the investigators based upon the 2014 NIH Consensus Development Project on Clinical Trials in cGVHD.

Response is assessed using individual scores from ten systems (Skin, Eyes, Mouth, Esophagus, Upper GI, Lower GI, Liver, Lungs, Joints and Fascia and Global Severity Rating (GSR)). Response is assessed with respect to the baseline (Cycle 1, Day 1 (C1D1)) cGVHD assessment. The overall response at each assessment time point will be categorized as Complete Response (CR), Partial Response (PR), or Lack of Response (LR), where LR includes the response status of unchanged, mixed, or progression as defined in [Table 1](#).

The ORR is defined as the proportion of patients with a best response meeting the overall response criteria assessment of CR or PR at any post-baseline response assessment.

If a treated patient is lost to follow up without response assessment, this patient will be counted as a non-responder. Any response on and after new systemic cGVHD treatment will be censored as non-response.

Table 1: cGVHD Response Definitions

| Response | Definition |
|------------------------|---|
| Complete Response (CR) | Resolution of all manifestations of cGVHD in each organ or site. |
| Partial Response (PR) | Improvement in at least one organ or site without progression in any other organ or site. |
| Lack of Response (LR) | |
| Mixed (LR-M) | Complete or partial response in at least one organ accompanied by progression in another organ* |
| Unchanged (LR-U) | Outcomes that do not meet the criteria for complete response, partial response, progression or mixed response |
| Progression (LR-P) | Progression in at least one organ or site without a response in any other organ or site |

* Considered progression for the purposes of analysis

5.1.2. Secondary Efficacy Endpoints

Secondary efficacy endpoints include Duration of Response (DoR), Lee Symptom Scale Score (LSS), Response by Organ System, Time to Response, Time to Next Therapy, Corticosteroid Dose, Calcineurin Inhibitor (CNI) Dose, Failure Free Survival (FFS), Overall Survival (OS), Change in cGVHD severity using the Clinician-Reported Global cGVHD Activity Assessment, and Change in symptom activity using the cGVHD Activity Assessment Patient Self-Report.

DoR

Four definitions of DoR are as following:

The primary definition of DoR is the time from first documentation of response to the time of first documentation of deterioration from best response (e.g., CR to PR, or PR to LR).

The secondary definition of DoR is the time from first documentation of response to the time of first documentation of lack of response.

The tertiary definition of DoR is the time from first documentation of response to the time of initiation of new systemic cGVHD therapy.

The quaternary definition of DoR is the time from first documentation of response to the time of first documentation of lack of response (as the secondary definition) but with durations summed for multiple response / lack of response episodes.

The DoR will be reported only for responders. And the censoring rules in [Table 2](#) will be applied.

Lee Symptom Scale Score (LSS)

Lee cGVHD Symptom Scale will be assessed on Day 1 of Cycles 2-5, then on Day 1 of every other Cycle thereafter and EOT. The questionnaire consists 30 items of 7 domains: skin, eyes and mouth, breathing, eating and digestion, muscles and joints, energy, and emotional. Each question is scored 0, 1, 2, 3 or 4.

A domain score will be calculated for each domain by taking the mean of all items completed if more than 50% were answered and normalizing to a 0 to 100 scale. A summary score will be calculated as average of all domain scores if more than 50% of them are nonmissing. A higher score indicated more bothersome symptoms. 7 points difference on the summary score of cGVHD symptom scale was found to be clinically meaningful.

$Raw\ Score = (I_1 + \dots + I_m) / m$, m is the number of items have nonmissing value in a domain.

$$Domain\ Score = Raw\ Score / 4 * 100.$$

$Summary\ Score = (Domain\ Score_1 + \dots + Domain\ Score_n) / n$, n is the number of domains have nonmissing domain scores.

Response by Organ System

Response assessment by physician for the nine individual organs (skin, eyes, mouth, esophagus, upper GI, lower GI, liver, lungs and joints and fascia) plus global severity rating will be collected in eCRF.

Time to Response (TTR)

TTR is defined as the time from first treatment to the time of first documentation of response.

Time to Next Therapy (TTNT)

TTNT is defined as the time from first treatment to the time of new systemic cGVHD treatment, censored by last response assessment or long term follow up assessment, which ever is the latest and available.

Corticosteroid Dose

Corticosteroid doses will be presented as mg/kg/day prednisone equivalent dose. If a patient is not using prednisone as the systemic corticosteroid, then the prednisone dose equivalent will be determined according to following conversion ratios:

1mg prednisone is equivalent to:

- 4mg Hydrocortisone
- 0.8mg Methylprednisolone
- 0.15mg Dexamethasone

- 1mg Prednisolone
- 0.8mg Triamcinolone

Transient increase in corticosteroid dosing (not exceeding 1mg/kg/day prednisone equivalent) is permitted for the treatment of cGVHD flare, but dose must be reduced back to the pre-enrollment dose within 6 weeks. If the dose remains elevated for more than 6 weeks, this will be considered a BN101/belumosudil treatment failure. More than 2 episodes of cGVHD flare requiring increased corticosteroid in the first month of BN101/belumosudil treatment will also be considered a BN101/belumosudil treatment failure.

Calcineurin Inhibitor (CNI) Dose

CNI includes systemic tacrolimus and cyclosporine.

Failure Free Survival (FFS)

FFS is defined as the absence of new cGVHD systemic therapy, non-relapse mortality and recurrent malignancy (e.g. underlying disease) and is censored by last response assessment or long term follow up assessment, whichever is the latest and available.

Overall Survival (OS)

OS is defined as time from first dose of BN101/belumosudil to the date of death due to any cause.

Change in cGVHD severity using the Clinician-Reported Global cGVHD Activity Assessment

The Clinician-reported global cGVHD Activity Assessment is a 0-10 point numeric rating scale with a score 0 indicating “cGVHD symptoms not at all severe” and a score of 10 being “most severe cGVHD symptoms possible”. The activities are assessed on Day 1 of each cycle from Cycle 1 Day 1 to EOT.

Change in symptom activity using the cGVHD Activity Assessment Patient Self-Report

The symptom activity item is a 0-10-point numeric rating scale with a score of 0 indicating “cGVHD symptoms not at all severe” and a score of 10 being “most severe cGVHD symptoms possible”. The status reported by patients are categorized as none, mild, moderate, and severe. The comparison of cGVHD symptoms to a month ago will also be reported by patients, rating from -3 (very much worse) to +3 (very much better).

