Eligible subjects will be enrolled to receive BN101/belumosudil (every 28-day cycle) until cGVHD progression [Evaluated by the investigator based on the National Institutes of Health (NIH) Consensus Development Project on Criteria for Clinical Trials in cGVHD(2014) diagnosis and staging, and response criteria, hereinafter referred to as the NIH Consensus Criteria (2014)], intolerable toxicity, initiation of a new cGVHD therapy, recurrence of hematological neoplasm (according to the recurrence criteria of the corresponding primary hematologic tumor), loss to follow-up, withdrawal of consent, or death, etc., whichever occurred first.

For subjects assessed as "Lack of Response - Mixed" and "Lack of Response - Progression" (See

section 7.1.1, table 4), if the investigator believed that these subjects could continue to benefit from treatment with BN101/belumosudil, the treatment may be continued after a written application was submitted, and approval from the Sponsor's Medical Director as well as documentation of the subject's willingness to continue treatment was obtained. In such cases, the rationale for continuing treatment must be clearly documented. In addition, "Lack of Response - Mixed" will be considered a progression event in the analysis of outcomes.

For subjects who did not achieve any response after 12 cycles of BN101/belumosudil treatment during the main study (the end of the main study is defined in section 3.5 of the main body), they should discontinue the investigational product treatment and withdraw from the study if they were judged by the investigator to have no clinical benefit (e.g., improvements in organ score, improvements in Lee symptom scores, reductions of corticosteroid/tacrolimus doses).

(1) Completion of study drug therapy

- Completion of study drug therapy as defined by the protocol;
- cGVHD disease progression during treatment;
- Death of the subject.

(2) Early termination of study drug therapy

Refers to the situation in which an enrolled subject becomes unfit to continue treatment with the study drug during the course of the study. Early termination of study drug treatment is defined as follows:

- Recurrence of the subject's hematologic tumor during the course of the trial (according to the criteria for recurrence of the corresponding primary hematologic tumor).

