Data lock and primary analysis will be performed 6 months after enrollment of the last subject. All subjects will continue to be followed up for an additional 6 months after the primary analysis as required by the protocol, i.e., the study will end 12 months after enrollment of the last subject, and a follow-up analysis will be performed at the end of the study. Subjects who have not yet experienced cGVHD progression at the end of the study, and in the judgment of the investigator, the benefits of continued dosing outweigh the risks, the sponsor will continue to provide BN101/belumosudil medication at no cost until cGVHD progression, intolerable toxicity, initiation of a new cGVHD therapy, recurrence of hematological neoplasm, loss to follow-up, withdrawal of consent, or death, etc., whichever occurred first.

Serious adverse events (SAEs), study drug use, and subject survival will continue to be collected for subjects who continue to be free of charge while the study drug, BN101/belumosudil, is administered at the end of the study.

Subjects who have not terminated BN101/belumosudil treatment at the end of the main study will

have a uniform end-of-treatment visit at the end of the main study.

AEs that remain at the end-of-treatment visit will be subject to continued follow-up, and all SAEs and AEs related to study treatment will be subject to follow-up until the event is resolved and the investigator considers the event to be stabilized or irreversible.

Twelve subjects at the designated centers will receive dense PK blood collection and the remaining subjects will receive sparse PK blood collection.

The primary efficacy endpoint of the study was ORR, defined as the proportion of subjects evaluated as CR or PR according to the NIH Consensus Criteria (2014) at any one post-baseline assessment. Secondary efficacy endpoints included median Duration of Response (DOR), Change in Lee Symptom Scale Score, Response rate by organ system, Percentage of subjects with best efficacy as PR and percentage of subjects with best efficacy as CR, Change in corticosteroid dose, Change in CNI dose, Failure-Free Survival (FFS), Overall Survival (OS), Change in cGVHD severity based on the Physician-Reported Global cGVHD Activity Assessment, and Change in symptom activity based on cGVHD Activity Assessment Patient Self-Report.

Changes in the PROMIS Physical Psychological Functioning Global Health Score will be analyzed as an exploratory endpoint of this study.

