10.6.2.2 Secondary Efficacy Endpoints

Secondary endpoints are as follows:

- DoR, defined as the time from the first evaluation of CR or PR to the confirmed occurrence of cGVHD progression. For subjects who had not experienced cGVHD progression at the end of the study, the date of their last objective evaluation was used as the DoR censoring date.
- Changes in the Lee Symptom Scale Score: Analyses will include:
 - Number of subjects with a \geq 7 point reduction
 - Number of subjects with a \geq 7 point reduction on 2 consecutive assessments
 - Duration of a \geq 7 point reduction
- Response by organ system: The response assessment for the nine individual organs (Skin, Eyes, Mouth, Esophagus, Upper GI, Lower GI, Liver, Lungs, and Joints and fascia).
- Number and percentage of subjects who have a best response of PR and number and percentage of subjects who have a best response of CR.
- Change in corticosteroid dose
- The prednisone equivalent dose of corticosteroids (mg/kg/day) during the study will be analyzed.
- Change in calcineurin inhibitor dose.
- FFS, FFS is defined as the absence of cGVHD treatment change, non-relapse mortality and recurrent malignancy. Median FFS (from first dose of BN101/Belumosudil) and landmark FFS at 1 year(if applicable) will be analyzed.
- OS, defined as time from first dose of BN101/belumosudil to the date of death due to any
 cause.
- Changes in cGVHD global severity rating using the Clinician-Reported Global cGVHD Activity Assessment
- Changes in symptom activity using the cGVHD Activity Assessment Patient Self-Report

Descriptive statistics will be provided for all secondary endpoints.

For DoR (only for subjects determined to have CR and/or PR), FFS, and OS, the median, first quartile, third quartile, and their two-sided 95% CIs were calculated using the Kaplan-Meier method, and survival curves were plotted.

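### The SAP reports DoR under four definitions, but none is the protocol's time from first response to confirmed cGVHD progression, and the departure is not recorded

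*SAP*

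**What the plan says.** **Protocol.** Section 4.1 names the endpoint: "Secondary efficacy endpoints included median Duration of Response (DOR"). Section 10.6.2.2 defines it: "DoR, defined as the time from the first evaluation of CR or PR to the confirmed occurrence of cGVHD progression". For subjects without progression at the end of the study, "the date of their last objective evaluation was used as the DoR censoring date". Section 3.3 says that a mixed response "will be considered a progression event in the analysis of outcomes", and the footnote to Table 4 in section 7.1.1 agrees. Table 4 defines LR-U as an outcome that is neither response, progression nor mixed. Progression for analysis is therefore LR-P or LR-M.

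**SAP.** Section 5.1.1 defines lack of response broadly, "where LR includes the response status of unchanged, mixed, or progression as defined in" its Table 1. Section 5.1.2 then gives four DoR definitions, all starting at first documented response:

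- Primary: ends at "the time of first documentation of deterioration from best response (e.g., CR to PR, or PR to LR").
- Secondary: "The secondary definition of DoR is the time from first documentation of response to the time of first documentation of lack of response".
- Tertiary: "the time from first documentation of response to the time of initiation of new systemic cGVHD therapy".
- Quaternary: as the secondary, with durations added over repeated episodes.

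Table 2 counts initiation of new systemic cGVHD therapy and death as events under all four. Section 8.4.2 promises Kaplan-Meier plots, descriptive statistics and landmark percentages for DoR.

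**The concern.** The terminating event is what defines a duration endpoint. If no SAP definition stops at progression, the study report will contain a median DoR that is not the quantity the protocol calls by that name. Nothing in the SAP tells the reader that the definition changed, or why. No other SAP time-to-event endpoint recovers it: FFS uses new therapy, non-relapse mortality and recurrent malignancy; TTNT uses new therapy; OS uses death.

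The difference is one of meaning. Under the SAP primary and secondary definitions, DoR measures how long a response is held. Under the protocol, it measures how long after first response a patient goes without getting worse. A reader of the report needs to know which was estimated, and that the choice was made before the data were seen. That matters more here because the trial is open-label with investigator-assessed response.

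**Working it through.** Neither document states a figure to reproduce, so the check is a comparison of event sets.

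| Definition | Events | Added to protocol set | Missing from it |
|---|---|---|---|
| Protocol 10.6.2.2 | LR-M, LR-P | – | – |
| SAP primary | CR to PR, LR-U, LR-M, LR-P, new therapy, death | CR to PR, LR-U, new therapy, death | none |
| SAP secondary | LR-U, LR-M, LR-P, new therapy, death | LR-U, new therapy, death | none |
| SAP tertiary | new therapy, death | new therapy, death | LR-M, LR-P |
| SAP quaternary | as secondary, episodes summed | LR-U, new therapy, death | none, but time is accumulated differently |

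No row matches the first.

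**Direction.** The primary and secondary definitions keep every protocol event and add others. For a given patient, the event therefore comes no later than under the protocol. This takes best response to mean best response to date, and it sets aside date rules: Table 2 back-dates some events after two or more missed assessments, and the documents do not share one censoring rule. The tertiary and quaternary definitions can run longer than the protocol's.

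**A constructed patient on the scheduled visits.** Suppose PR at Cycle 2 Day 1, organ scores back at baseline (LR-U) at Cycle 5 Day 1, and LR-P at Cycle 9 Day 1, with no new therapy or death in between. Cycles last 28 days.

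- SAP primary and secondary: (5 − 2) × 4 = 12 weeks.
- Protocol: (9 − 2) × 4 = 28 weeks.
- SAP quaternary: 12 weeks (one episode).
- SAP tertiary: no event yet at 28 weeks.

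**Why no trial-level size can be given.** Let f be the share of SAP-secondary events that are LR-M or LR-P. With constant hazards, and progression risk unaffected by the other events, the protocol median divided by the SAP-secondary median is 1/f:

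- f = 0.9: 1/0.9 = 1.1
- f = 0.7: 1/0.7 = 1.4
- f = 0.5: 1/0.5 = 2.0
- f = 0.3: 1/0.3 = 3.3
- f = 1: no difference

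The documents give no value for f, and the model itself is doubtful. Take f = 0.5, let every other event be LR-U, and let the progression hazard double after LR-U. With the total SAP hazard set to 1, the protocol curve is S(t) = exp(−t)(1 + 0.5t), which reaches 0.5 at t = 1.146. The SAP median is ln 2 = 0.693, so the ratio is 1.146/0.693 = 1.65 rather than 2.0. These ratios only show how sensitive the result is to unknown inputs; they do not predict the gap.

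**Which added events matter.** Protocol 1.4.2 reports CR in 4.5% of the 200 mg QD group of KD025-213. If that held here, 30 × 0.045 = 1.35, so about one patient could contribute a CR-to-PR event. Any gap would then come mainly from LR-U, new therapy and death.

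**The case against.** **The secondary definition is close.** It is: it equals the protocol's when no responder has LR-U, new therapy or death before progression. Nothing ensures that, and the SAP's primary definition is further away.

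**The SAP is conservative.** For the primary and secondary definitions this is right: the added events cannot flatter the drug. That answers a charge of bias, not one of reporting a different endpoint.

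**New therapy belongs among the events.** This has force. Protocol 6.4 treats new systemic cGVHD therapy as failure of study treatment, while 10.6.2.2 is silent on new therapy and on death. Neither document says what makes progression confirmed. The protocol text cannot be programmed as it stands, so copying it into the SAP would not be enough.

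**The SAP is where methods are detailed.** Protocol 10.1 says so, but replacing the terminating event goes beyond detail.

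**The SAP already ranks its definitions.** It does label one primary. It does not say that this is the protocol's median DOR, or that it differs from 10.6.2.2.

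**Stronger readings to avoid.** A reader might infer that no DoR will be produced; section 8.4.2 of the SAP shows otherwise. A reader might stretch the overseas medians in Protocol 1.4.2 (21.1 weeks in the KD025-213 200 mg QD group, 35 weeks in KD025-208) by the ratios above, or conclude that the SAP spoils the bridging comparison. The protocol does not say how either median was defined, so neither step is supported. The SAP may follow the overseas definition, but it does not say so. Being listed first also gives DoR no formal rank: no hierarchy is stated, and SAP section 6 makes all analyses descriptive.

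**Conclusion.** The mismatch stands. Followed as written, the SAP reports DoR four ways and never as protocol 10.6.2.2 defines it, with no record of the departure. The primary and secondary results will equal or understate the protocol-defined DoR, apart from date-setting rules. By how much cannot be determined from the documents: it could be nothing if responders lose response only through LR-M or LR-P, and it grows with the share who reach LR-U, new therapy or death first.

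The conclusion rests on reading progression as LR-P plus LR-M, which Protocol 3.3 and Table 4 support, and on reading LR in the SAP as including LR-U, which section 5.1.1 states. It is a consistency fault in a descriptive secondary endpoint. It does not touch ORR, and harm to the comparison with KD025-213 is not shown. It should still be settled before lock, because a choice among definitions made afterwards would look data-driven.

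**What to change.** Before database lock, do one of the following:

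1. Add the protocol-defined DoR to SAP 5.1.2 and Table 2 as a further Kaplan-Meier analysis with LR-M and LR-P as events and censoring at the last objective evaluation. State what confirmed means and how new systemic therapy and death are handled.
2. Amend protocol 10.6.2.2 to the SAP primary definition and record the reason.

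In either case, state in the SAP which definition is the protocol's median DOR endpoint. Where the report cites an overseas median, give that median's definition beside it.

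The cost is SAP wording and one more table, or a protocol amendment. No new data are needed: LR is already classified as unchanged, mixed or progression at each response assessment.

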4.3.6 Long-Term Safety Follow-Up

Subjects who terminate study treatment early before the end of the main study will be contacted by telephone by the study center approximately every 12 weeks to confirm their survival, any changes in cGVHD treatment, and any antitumor therapy until the end of the main study (see Section 3.5).

Subjects who have not yet experienced cGVHD progression at the end of the study, and in the judgment of the investigator, the benefits of continued dosing outweigh the risks, may submit a written request and, upon approval by the sponsor's Medical Director and documentation of the subject's willingness to continue the treatment, the sponsor will continue to provide BN101/belumosudil medication at no cost until cGVHD progression, intolerable toxicity, initiation of a new cGVHD therapy, recurrence of hematological neoplasm, loss to follow-up, withdrawal of consent, or death, etc., whichever occurred first. During this period, subjects will return to the study center in accordance with their clinical practice, and the study will continue to collect SAEs, study drug use, and survival (or can be contacted by phone). In addition, SAEs for this group of subjects will need to be collected up to 28 days (±7) after the last dose or the initiation of new cGVHD therapy.

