The best response (CR, PR) for the nine individual organs plus global severity rating will be summarized. Time to response at the organ level will also be evaluated. Descriptive statistics and plots of cumulative number and percentage of responders over time will be provided. Two series of percentages will be presented:

- With total number of patients in mITT with involvement of the given organ at baseline as denominator
- With numbers of patients in the responder population with involvement of the given organ at baseline as denominator

Time to Response (TTR)

Descriptive statistics and plots of cumulative number and percent of responders over time will be provided. TTR analyses will only be conducted for the responder population.

Time to Next Therapy (TTNT)

TTNT will be analysed by the Kaplan-Meier survival method as well as the landmark analysis at 3, 6, 9, and 12 months.

Corticosteroid Dose

Corticosteroid doses will be presented as prednisone equivalent dose. Descriptive statistics for the mITT population, responder / nonresponder populations will be provided for:

- Systemic corticosteroid dose over time
- Change and percent change from baseline (C1D1) to the greatest corticosteroid dose reduction during BN101/belumosudil treatment period
- Number and percentage of patients who reduced systemic corticosteroid dose during BN101/belumosudil treatment period
- Number and percentage of patients who ever discontinued systemic corticosteroid usage for over 28 days during BN101/belumosudil treatment period

The above analyses will be censored on or after new systemic cGVHD treatment.

Calcineurin Inhibitor (CNI) Dose

CNI includes systemic tacrolimus and cyclosporine. Descriptive statistics will be provided for:

- Number and percentage of patients who reduced CNI dose during BN101/belumosudil treatment period
- Number and percentage of patients who ever discontinued CNI during BN101/belumosudil treatment period

Failure Free Survival (FFS)

Kaplan-Meier plots, descriptive statistics of FFS and landmark FFS at 3, 6, 9, and 12 months will be provided. In addition, analyses for the three components of FFS will also be provided.

Overall Survival (OS)

Kaplan-Meier plots, descriptive statistics of OS and landmark OS at 3, 6, 9, and 12 months will be provided.

Change in cGVHD severity using the Clinician-Reported Global cGVHD Activity Assessment

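### Time to next therapy censors patients who die, so Kaplan-Meier can slightly overstate how many start new therapy

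*SAP*

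**What the plan says.** SAP 5.1.2 gives time to next therapy (TTNT) a single event: "TTNT is defined as the time from first treatment to the time of new systemic cGVHD treatment, censored by last response assessment". In full, everyone without that event is "censored by last response assessment or long term follow up assessment, which ever is the latest and available". SAP 8.4.2 gives the method: "TTNT will be analysed by the Kaplan-Meier survival method as well as the landmark analysis at 3, 6, 9, and 12 months". Neither section has a rule for death without new therapy, and neither mentions a cumulative incidence method.

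Two neighbouring endpoints treat death differently. Tertiary duration of response (DoR) also runs to new systemic cGVHD therapy, and SAP Table 2 lists death among its events. For failure-free survival (FFS), "FFS is defined as the absence of new cGVHD systemic therapy, non-relapse mortality and recurrent malignancy". SAP 8.4.2 adds that "analyses for the three components of FFS will also be provided" and names no estimator for them.

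On follow-up, Protocol 3.3 lists "Recurrence of the subject's hematologic tumor during the course of the trial" as a reason to end study drug early, after which the subject enters safety follow-up, including the long-term part. Under Protocol 4.3.6, subjects who stop early are telephoned "approximately every 12 weeks to confirm their survival, any changes in cGVHD treatment, and any antitumor therapy until the end of the main study".

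**The concern.** Kaplan-Meier treats a censored patient as having the same future chance of the event as those still under observation. That is reasonable for a patient whose follow-up has simply ended. A patient who has died cannot start new therapy. Censoring the death removes the patient from the risk set and in effect shares that patient's probability among the survivors. Each later new-therapy start then counts for slightly too much, so one minus Kaplan-Meier (1-KM) is never below the actual proportion starting new therapy and exceeds it once a death comes before a later start.

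Two things are at stake. The landmark TTNT figures will probably be read as the proportion of patients needing another systemic treatment. The same report would also treat death before new therapy as an event in one endpoint, a failure (if non-relapse) in another and censoring in a third, without explanation. The FFS components raise a related question: if each were run by Kaplan-Meier, they would not add up to their own composite.

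**Working it through.** **Nothing to reproduce.** The documents give no TTNT rate or death rate, and Protocol 10.2 says the sample size of 30 does not rest on statistical assumptions. All rates below are assumptions, shown as a range.

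**1. Who is censored.** A patient who dies without new therapy has no event and is censored at the last assessment or contact. A relapsed patient stops study drug, but cGVHD treatment changes are still recorded and TTNT censoring waits for the latest contact. That patient stays at risk, and later new cGVHD therapy counts.

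**2. Size under constant hazards.** Let q be the 12-month new-therapy probability by 1-KM and d the 12-month probability of death before new therapy, each net of the other. Then a = -ln(1-q), b = -ln(1-d), and

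cumulative incidence = a/(a+b) × (1 - exp(-(a+b))).

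For q = 40%, a = 0.5108.

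- d = 5%: b = 0.0513 and a/(a+b) = 0.9088. The second factor is 1 - 0.60 × 0.95 = 0.430. Result: 39.1%, an excess of 0.9 points.
- d = 10%: b = 0.1054 and a/(a+b) = 0.8290. The second factor is 1 - 0.60 × 0.90 = 0.460. Result: 38.1%, an excess of 1.9 points.

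Cumulative incidence at 12 months:

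| 1-KM | d = 0 | d = 5% | d = 10% | d = 20% |
|---|---|---|---|---|
| 20% | 20.0% | 19.5% | 19.0% | 18.0% |
| 30% | 30.0% | 29.3% | 28.6% | 27.1% |
| 40% | 40.0% | 39.1% | 38.1% | 36.2% |
| 50% | 50.0% | 48.9% | 47.7% | 45.4% |

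**3. The order of events matters.** Take 30 patients with complete follow-up: 9 start new therapy (9/30 = 30.0%) and 2 die without it. If both deaths come first, 1-KM is 9/28 = 32.1%. If they are interleaved with the starts, it is 31.4%. If both come after the last start, it is 30.0%, with no excess.

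**4. Against sampling error.** In 5,000 simulated trials of 30 patients with full 12-month follow-up and q = 40%:

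- d = 5% (about 1.2 deaths): mean excess 0.9 points; standard deviation of 1-KM 9.0 points.
- d = 10% (about 2.4 deaths): mean excess 1.9 points; standard deviation 9.3 points.

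A binomial check agrees: √(0.40 × 0.60/30) = 8.9 points.

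**5. FFS components.** These are first failures, so relapse does compete here. Assume 12-month 1-KM values of 40% (new therapy), 10% (non-relapse death) and 10% (relapse). They sum to 60%, whereas 1-FFS = 1 - 0.60 × 0.90 × 0.90 = 51.4%. With hazards 0.5108, 0.1054 and 0.1054, the cumulative incidences are 36.4%, 7.5% and 7.5%, which sum to 51.4%.

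**The case against.** Kaplan-Meier with deaths censored is a recognised cause-specific summary, and the SAP does not say that 1-KM will be presented as a cumulative incidence. FFS and overall survival (OS) are planned at the same four landmarks, so the report will show deaths. Entry requires life expectancy above 12 months and ECOG 0 to 1 (Protocol 3.1), so deaths before new therapy may be few. TTNT is not among the protocol's secondary endpoints (7.1.2, 10.6.2.2), and SAP section 6 makes all analyses descriptive. All of this stands and limits the weight of the point. It does not supply a rule for death, and a landmark figure is likely to be read as a proportion of patients.

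A reader might go further and infer that relapse is also handled as censoring in TTNT. The documents do not support that: the censoring rule includes long-term follow-up, which continues to record cGVHD treatment changes after study drug stops. A reader might also infer that the component figures will fail to add up to 1-FFS. That follows only if Kaplan-Meier is used for each, and the SAP names no method. Nor must TTNT itself reconcile with FFS, because new therapy after relapse is a TTNT event while FFS has already failed at relapse.

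**Conclusion.** The point holds for death only, and conditionally. As planned, TTNT overstates the proportion starting new therapy if at least one patient dies without it before another patient starts. Without such a death the excess is zero. With 1-KM of 40% and 5% to 10% deaths it is about 1 to 2 points. Across the table (1-KM of 20% to 50%, deaths of 5% to 20%) it runs from 0.5 to 4.6 points. These sizes rest on assumed rates and constant hazards, and all lie below the sampling standard deviation of about 9 points found at n=30 with 1-KM of 40%. An unconditional statement that the TTNT figures are biased would therefore go too far.

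This is a low-priority improvement to a descriptive secondary endpoint. It is still worth making: the direction of the error is known, the study's purpose is a descriptive comparison with KD025-213, and the SAP currently treats death in different ways without saying why.

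**What to change.** In SAP 5.1.2 and 8.4.2, state how death without new therapy is handled in TTNT. Report TTNT at 3, 6, 9 and 12 months as an Aalen-Johansen cumulative incidence with that death as the competing event. Say explicitly that relapsed patients are followed through and that their later new cGVHD therapy counts; making relapse a competing event would change what TTNT measures.

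For the three FFS components, name cumulative incidence of the first failure, with the other failure types competing, so that they sum to 1-FFS. Keep Kaplan-Meier for FFS and OS.

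The cost is a few sentences of SAP wording and one extra analysis. No new data are needed, because survival and cGVHD treatment changes are already collected. If Kaplan-Meier TTNT is wanted for comparison with KD025-213, it can be shown alongside.
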